Study Protocol and Statistical Analysis Plan

Document Date: May 4, 2018

ID: NPSASA-14-321959      Impact of Combined Behavioral Interventions on Cognitive  
NCT: 02864069                      Outcomes in MCI

**SPECIFIC AIMS/HYPOTHESES:** Primary Aim: Compare the efficacy of participating in singular [(walking *or* computer training (CT)] vs. combined (walking *and* CT) behavioral interventions in maintaining/ improving cognitive functioning, quality of life (QOL), and daily functioning, in 60 adults with mild cognitive impairment (MCI) or cognitive complaints, ages 55-80. Primary hypotheses: 1: The combined group will show greater cognitive benefits (objective neuropsychological and ecological measures of cognition) 0- and 3-months post-intervention than either singular intervention group. 2: The combined group will have greater QOL benefits (patient and informant self-report) and maintenance of independent functioning (Independent Living Scales; ILS, CDR) 0- and 3-months post-intervention than either singular intervention group. Secondary Aim: Compare any differential cognitive benefits of physical vs. cognitive interventions. Secondary hypothesis: Walking will result in greatest benefits to executive functioning while CT will result in greatest benefits to memory.

**EXPERIMENTAL DESIGN AND METHODS:** *Participants.* We will recruit 60 largely sedentary (< 1 hour/week of purposeful aerobic exercise for the past 6 months), though otherwise medically healthy, participants with MCI or cognitive complaints, ages 55-80. Participants will be randomized to the walking intervention (n=20), a CT program (n=20), or a combined walking and CT intervention (n=20). Participants will be recruited from the Memory and Aging Resilience Center (MARC), the Alzheimer's Disease Research Center (ADRC) and multiple existing studies of aging at the University of California, San Diego (UCSD) who consented to be contacted about other studies. We will over-recruit by 10% to account for subject attrition and to ensure a final sample size of 60. These sources should allow for realistic attainment of the desired sample size and recruiting from these extant sources is optimal given that many have already been screened for general health and gross cognitive status. Should these recruitment avenues be insufficient, however, additional community participants will be recruited. All participants will be screened and excluded if they have a history of significant head trauma, other neurologic or major psychiatric disorders, known dementia, current substance dependence, or any contraindication to increased physical activity. Participants must also be fluent in English, willing to commit to the time requirements of their assigned intervention, and be free of sensory or mobility deficits that would interfere with the interventions. Participants not showing sufficient adherence to their intervention protocol will be discontinued from the study. If not administered by the recruitment source in the last 6-weeks, the Montreal Cognitive Assessment (MoCA) and the Clinical Dementia Rating Scale (CDR) will be included in the screening; MoCA must be 18-30 and CDR of 0 or 0.5 at entry into the study. Participants cannot be engaged in another cognitive training or exercise trial during participation during this investigation. Individuals over age 80 will not be included due to increased risk of mobility difficulties and safety concerns in the oldest-old with the walking protocol.

*Procedures:* Appropriate individuals who agree to participate will provide informed consent. Although participants will be screened for inclusion/exclusion criteria prior to study entry, if during the course of any of the following assessments exclusionary information becomes available, that participant's data will not be analyzed. Dementia is exclusionary at baseline, however, if future assessments reveal that a participant has transitioned to dementia, their data will be utilized. We will reduce participant burden and practice effects and maximize use of data already available from our recruitment avenues; if participants have undergone neuropsychological testing within six weeks of their scheduled baseline assessment, we will request their prior test results to use as part of their baseline evaluation and only administer tests

not previously given. All participants will obtain medical clearance by a physician to participate in the protocol and provide basic medical information (including medical history, basic health and fitness variables, stroke risk factors, blood pressure, height, weight, and body mass index). All participants will undergo neuropsychological assessment on three occasions: a baseline assessment, immediately post-intervention (0-month post), and extended follow-up at 3-months post-intervention (3-month post). Based on prior research, the assessment measures were chosen to cover executive functioning and memory, daily functioning, and informant report of functioning, in particular. Ecological measures of cognition are also included to be able to determine generalizability and impact on everyday functional skills. The baseline assessment will entail a comprehensive neuropsychological exam consisting of measures of global cognitive functioning and estimated premorbid intellectual functioning (American National Adult Reading Test; ANART) the Wechsler Abbreviated Scale of Intelligence (WASI), language (the Boston Naming Test (BNT), memory (Hopkins Verbal Learning Test (HVLT), executive functioning [selected subtests from the Delis Kaplan Executive Functioning System (DKEFS)], attention/working memory from WAIS-IV: Symbol Search, and Digit Span, Symbol-Digit Modalities Test (SDMT), the CDR, and an ecologically valid assessment of cognitive functioning (Rivermead Behavioural Memory Test; RBMT) that will test some skills specifically trained in the CT condition (e.g., name learning, and story learning) but also additional untrained skills such as prospective memory. We will also administer the ILS, a practical measures of functional living skills (Loeb, 1996), the Everyday Cognition Scale (ECog), an informant-based questionnaire of everyday cognitive skills with multiple scales covering memory, language, visuospatial abilities, executive functioning, and divided attention (Farias et al., 2008), a self-report measure of mood (the Geriatric Depression Scale), a measure of QOL, the Quality of Life Interview-Brief Version [QOLI-Brief (Lehman, Kernan, & Postrado, 1994)], and a self-report assessment of current and past physical activity including the Community Health Activities Monitoring Program for Seniors (Stewart et al., 2001).

The walking intervention will begin following baseline assessments and will be continued for 12 weeks. The walking group will be given a pedometer (a small, unobtrusive device, clipped to a waistband or put in a pocket that saves step data for one week, and should not impede normal daily activities) to use daily and log their daily steps, with an identified goal of increasing step counts by 3000 steps a day over the course of the intervention. After obtaining a weeklong baseline step count, individuals in the intervention group will be placed on a program to progressively increase their step counts by 100 steps daily each week for the first three weeks, by 200 steps daily for weeks four through six, by 300 steps daily for weeks seven through nine, and by 400 steps daily for weeks ten through twelve. These are cumulative step increases so that participants will increase average daily step counts by 3000 steps over the course of the intervention. Mean baseline step counts for sedentary older adults in our pilot work were 4150 per day; therefore, most participants will almost double their daily activity by the end of the intervention. To guide participants and maintain adherence to the study protocol, the study coordinator will contact the participants weekly to discuss activity logs and adjust step goals. The study coordinator will also be available via phone throughout the study to answer questions that may arise.

In the CT condition, participants will use Brain HQ, a computer cognitive training program (Posit Science Corporation, San Francisco, CA), shown to be well tolerated by older adults with positive short and long-term cognitive outcomes (Rebok et al., 2014; Smith et al., 2009). Participants will complete 6 Brain HQ modules: 'To Do List Training,' dedicated to verbal

memory, 'Syllable Stacks,' a working memory module, 'Divided Attention,' 'Mixed Signals,' targeting inhibition, 'In the Know,' for story learning, and 'Face Facts,' for name learning. Participants will use the program 60 minutes/day, 5 days/week for 12 weeks. They will receive a brief introduction to the program on site at the MARC (log-in, which modules to complete, and how long to spend each day on CT). These instructions will then be repeated via phone once the participant is on their home computer and can be supplemented by an in-home visit if significant technological difficulties exist. If participants do not have a home computer/internet access, they can complete the modules at another location such as a public library, senior center, or at the MARC, but training will still be self-directed. Brain HQ offers a secure clinician portal that allows for monitoring of usage and progress of participants but the study coordinator will still be in weekly phone contact with participants to discuss activity logs and answer any questions.

The combined condition will concurrently follow both the walking and the CT programs as described above.

*STATISTICAL ANALYSES:* Assuming a one tailed test, a medium effect size with power of .7 can be obtained with the sample size of 20 per group. The groups will be compared on baseline characteristics, including program adherence, using t-tests and  $\chi^2$  and analyses will be adjusted to account for any observed group differences. Lifestyle covariates such as health, prior physical activity, mood, and education will also be explored and used as appropriate. We will employ reliable change analyses to take into account change in neuropsychological test scores over the course of the intervention while also accounting for predicted practice effects. To address the primary hypothesis, group comparisons of changes in neuropsychological test scores and measures of daily functioning between the groups will be determined via ANCOVA and repeated measures analyses. For the CT condition in particular, we will examine whether any cognitive benefits generalize beyond the trained task. To address the secondary hypothesis, we will use logistic regression to determine the degree to which intervention group predicts differential cognitive outcomes. Correlations between neuropsychological test scores and health and fitness variables will also be explored.

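### Low adherers are discontinued from the study after randomisation, and a second rule can drop data later, with no follow-up of those removed and no analysis as randomised.

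*Combined protocol and SAP*

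**What the plan says.** The combined protocol and SAP touches on this point in five places.

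- **Participants:** "Participants not showing sufficient adherence to their intervention protocol will be discontinued from the study". The removal is from the study, not only from the program. No threshold, timing or assessor is given. The same paragraph over-recruits by 10% so as to finish with 60.
- **Procedures, first paragraph:** "if during the course of any of the following assessments exclusionary information becomes available, that participant's data will not be analyzed". One exception follows: "if future assessments reveal that a participant has transitioned to dementia, their data will be utilized".
- **Procedures, assessments:** "All participants will undergo neuropsychological assessment on three occasions: a baseline assessment, immediately post-intervention (0-month post), and extended follow-up" at 3 months. Nothing says whether this still applies to someone already discontinued.
- **Combined condition:** "The combined condition will concurrently follow both the walking and the CT programs as described above". That means progressive daily step goals plus computer training (CT) of 60 minutes a day, five days a week, for 12 weeks. Each single arm follows one of these.
- **STATISTICAL ANALYSES:** "The groups will be compared on baseline characteristics, including program adherence", with adjustment for any group differences found. The section names ANCOVA, repeated measures, reliable change and logistic regression. It names no analysis set, no analysis by assigned group and no missing-data method.

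**The concern.** Both primary hypotheses compare the combined arm with each single arm. Randomisation protects those comparisons only if people stay in the group to which they were assigned. Removing low adherers replaces the randomised groups with groups selected on behaviour that the assigned program itself influences.

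There are two reasons to expect unequal removal. The combined arm has two programs in which to fall short. Adherence is also observed differently: walking through participants' own step logs, CT through logs and a usage portal. If better adherers also tend to have better outcomes, removing more people from the combined arm raises its mean without any treatment effect, in the direction that the primary hypotheses predict.

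The analysis section does not repair this. Adherence is not a baseline characteristic; adjusting for it conditions on a consequence of assignment and cannot recover outcomes that were never collected. The over-recruitment restores the number of participants, not the comparability of the arms.

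The second rule does not select on adherence. It may be meant only for ineligibility that screening missed. However, it applies at assessments that include the two post-intervention visits, and the exception for new dementia suggests that other new conditions could lead to removal.

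**Working it through.** **What the documents supply.** They give 20 per arm, a one-tailed test, and 10% over-recruitment: 60 × 1.10 = 66 recruited, or 22 per arm, so a planned loss of 6/66 = 9.1% from all causes. They give no adherence rates, no link between adherence and outcome, and no alpha. There is therefore no plan figure for this bias to reproduce. What follows is an illustration.

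**Assumptions.** No true effect; outcome SD 1; one-sided alpha 0.05 (critical value 1.645); no covariate adjustment. Each program has a latent normal adherence score A and is adhered to if A > c, with probability p. In the combined arm the two scores have correlation ρ (0 to 1), and both programs must be adhered to. Outcome correlates r = 0.3 to 0.5 with each score.

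**Formulas.** φ is the standard normal density, and p_both is the probability of adhering to both programs.

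- Single-arm mean after removal: r·φ(c)/p
- Combined-arm mean after removal: [2r/(1+ρ)]·E[A1 | A1 > c, A2 > c]
- Bias: combined mean minus single mean
- SE = √(1/(20·p_both) + 1/(20·p))
- Type I error = P(Z > 1.645 − bias/SE)

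**Worked case, p = 0.90, ρ = 0, r = 0.5.**

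- c = −1.2816 and φ(c) = 0.1755, so φ(c)/p = 0.195.
- Single-arm mean = 0.5 × 0.195 = 0.097. With ρ = 0 the combined-arm mean is twice that, so the bias is 0.097 SD.
- p_both = 0.90² = 0.81, so 19% are removed from the combined arm and 10% from a single arm.
- SE = √(1/16.2 + 1/18) = 0.342.
- 1.645 − 0.0975/0.3425 = 1.360, which gives a type I error of 8.7%.

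| p per program | ρ | Removed, combined arm | Bias in SD (r = 0.3; 0.5) | One-sided type I error |
|---|---|---|---|---|
| 0.95 | 0 | 9.8% | 0.033; 0.054 | 6.1%; 6.9% |
| 0.90 | 0 | 19.0% | 0.058; 0.097 | 7.0%; 8.7% |
| 0.90 | 0.5 | 16.8% | 0.039; 0.065 | 6.3%; 7.3% |
| 0.90 | 0.8 | 14.4% | 0.023; 0.039 | 5.8%; 6.3% |
| 0.80 | 0 | 36.0% | 0.105; 0.175 | 8.6%; 11.9% |
| any | 1 | same as single arm | 0; 0 | 5.0%; 5.0% |

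A simulation of 4 million draws at p = 0.90 gave the same biases for ρ = 0 and ρ = 0.8.

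**Tied to the plan's own allowance.** Suppose all 6 planned losses are adherence removals and ρ = 0. Then (2p + p²)/3 = 60/66, so p = 0.931, and removal is 6.9% in a single arm and 13.4% in the combined arm. With 22 per arm, SE = 0.318, bias is 0.043 to 0.072 SD and type I error 6.6% to 7.8%. With ρ = 1, bias is 0.

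**Check with a simpler model.** Use one adherence score per person and remove the lowest 20% of the combined arm and the lowest 10% of a single arm. The bias is r × (0.350 − 0.195) = 0.155r, or 0.031 to 0.077 SD for r = 0.2 to 0.5. With 22 per arm, type I error is 6.1% to 8.0%. With equal 10% removal it is 5.0%.

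**The case against.** The strongest reply concerns size. The plan allows for about 9% loss from all causes. At 80% adherence per program, average removal across the three arms would be 20% to 25%, more than twice that; at 90% it would be 10% to 13%, also above it. Within the allowance, bias is at most about 0.07 SD under this model. Even 0.10 SD is only 0.29 of a standard error (0.0975/0.3425). The range for r is assumed, the lower bound is zero, and the sign is not established. The plan also supports adherence through weekly contact, step-goal adjustment, portal monitoring and in-home help, and it requires willingness to commit the time. The exclusion rule under Procedures opens by referring to screening before entry, so late-found ineligibility is its natural reading.

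Most of this stands as a limit on size. The 80% row should be read as lying beyond planned attrition. But the allowance is a planning figure, not an observed rate, and it does not cap removals under a rule with no threshold. Adherence support may reduce removals but does not stop those that occur from being selective. The statement that all participants are assessed three times does not say that it includes people already discontinued. The benign reading of the exclusion rule is fair, but its wording reaches the post-intervention visits, so it still needs clarifying.

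**Conclusion.** The concern holds. As written, the plan compares arms after a selection that follows randomisation, and nothing in the documents provides follow-up of those removed or an analysis by assigned group. This does not depend on the illustration.

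Size and direction are not known from the documents. At 90% adherence per program the illustration gives 0 to 0.10 SD and a one-sided type I error of 5.0% to 8.7%; at 95%, 0 to 0.05 SD and 5.0% to 6.9%. These ranges rest on equal adherence to each program, r between 0.3 and 0.5, and no covariate adjustment. Bias is proportional to r, so covariates that halved r would halve it. It is zero if removals are equal across arms and unselective, and it reverses if the combined arm loses fewer people.

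This must be fixed because the loss cannot be undone: once people leave without 0- and 3-month assessments, no later analysis has their outcomes.

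**What to change.** - **Participants.** Replace the discontinuation sentence with wording such as: *Participants with low adherence remain in the study for the 0- and 3-month assessments, whether or not they continue the program. The primary analysis includes all randomised participants in their assigned group. An adherent-only analysis, with adherence defined before outcome data are seen, is secondary.*
- **Procedures.** Limit exclusion of data to ineligibility that existed before randomisation, judged without knowledge of arm.
- **STATISTICAL ANALYSES.** Report program adherence by arm as a post-randomisation measure, and do not use it as a baseline covariate in the primary analysis.

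The cost is wording plus up to two assessments per person who would have been removed. That is 12 visits if all 6 planned losses were adherence removals. At 90% adherence with independent programs it is about 16 visits: 2 + 2 + 3.8 = 7.8 removed of 60, twice each. The estimate may be diluted relative to full adherers; the secondary analysis still shows the adherent-only estimate.

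### The stated power of .7 is not supported for the combined-versus-single contrasts: the inputs needed to check it are missing, and with one follow-up and usual assumptions it needs baseline adjustment and a correlation of about 0.7

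*Combined protocol and SAP*

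**What the plan says.** The power statement, under Statistical Analyses, is a single sentence: "Assuming a one tailed test, a medium effect size with power of .7 can be obtained with the sample size of 20 per group". No section gives an alpha level, a number for the effect, its scale, the test behind the figure, the visit, or a correlation between visits.

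The contrasts to be powered are set in Specific Aims/Hypotheses. The combined group "will show greater cognitive benefits (objective neuropsychological and ecological measures of cognition) 0- and 3-months post-intervention than either singular intervention group", and the second primary hypothesis has the same form for quality of life and independent functioning. Allocation, under Experimental Design and Methods, is equal: "Participants will be randomized to the walking intervention (n=20), a CT program (n=20), or a combined walking and CT intervention (n=20"). Attrition is handled separately: "We will over-recruit by 10% to account for subject attrition and to ensure a final sample size of 60".

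On analysis, Procedures states "All participants will undergo neuropsychological assessment on three occasions" (baseline, 0 months and 3 months post-intervention). Statistical Analyses says that group comparisons "of changes in neuropsychological test scores and measures of daily functioning between the groups will be determined via ANCOVA and repeated measures analyses". On covariates it says that "analyses will be adjusted to account for any observed group differences" and "Lifestyle covariates such as health, prior physical activity, mood, and education will also be explored and used as appropriate". The baseline score of the outcome under analysis is not named as a covariate.

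**The concern.** A reader who completes the power sentence with the usual conventions (d = 0.5 for medium, one-sided alpha 0.05) and applies it to 20 versus 20 gets well under one half, not .7. The planned ANCOVA or repeated-measures analysis can do better, but by how much depends on whether baseline is adjusted for and how strongly baseline and follow-up correlate. The plan fixes neither.

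At stake is how the result will be read. If true power per contrast is nearer one half than .7, a null comparison of combined with single intervention says much less than the protocol implies. The adjustment that would recover precision uses a score already collected, yet the plan does not commit to it.

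**Working it through.** **Inputs from the documents:** one-tailed test; medium effect; 20 per group; two contrasts (combined vs walking, combined vs CT); three assessments. The 10% over-recruitment is meant to leave 60 at the end, so n = 20 per arm is used.

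**Assumed, because not stated:** d = 0.5 in raw-score SD units; one-sided alpha 0.05; baseline-to-follow-up correlation r = 0.5 or 0.7.

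**Method:** power is the chance that a noncentral t variable exceeds the one-sided critical value. For two groups of 20 the noncentrality is d* × √(20/2) = 3.162 × d*, where d* is the effect divided by the SD of the quantity analysed.

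**1. Trying to reproduce .7 from the stated inputs (one visit, unadjusted).** d* = 0.5; noncentrality 3.162 × 0.5 = 1.581; df 38; critical value 1.686. Power = 46.3%.
- Other alphas: 33.8% at 0.025 and 61.1% at 0.10.
- With 22 per group: 49.5%.
- To reach .70 with this test: alpha of about 0.15, or d of about 0.70, or 39 per group.

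The stated figure is not reproduced.

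**2. Change score, one follow-up.** d* = d/√(2(1 − r)), df 38.
- r = 0.5: 0.5/√1.0 = 0.500; noncentrality 1.581; power 46.3%.
- r = 0.7: 0.5/√0.6 = 0.645; noncentrality 2.041; power 64.1%.
- .70 needs r of about 0.74.
- If medium is meant on the change-score scale itself, d* = 0.5 whatever r is, and power is 46.3% at any correlation.

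**3. Baseline-adjusted ANCOVA, one follow-up.** d* = d/√(1 − r²), df 37, critical value 1.687.
- r = 0.5: 0.5/√0.75 = 0.577; noncentrality 1.826; power 55.9%.
- r = 0.7: 0.5/√0.51 = 0.700; noncentrality 2.214; power 70.1%.
- A simulation allowing for chance baseline imbalance gives about one point less: 54.9% and 69.0%.

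| 20 vs 20, d = 0.5 raw SD, one-sided 0.05 | r = 0.5 | r = 0.7 |
|---|---|---|
| One visit, unadjusted | 46% | 46% |
| Change score, one follow-up | 46% | 64% |
| Baseline-adjusted ANCOVA, one follow-up | 56% | 70% |

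**4. An option the plan does not specify.** Suppose the outcome were the mean of both follow-ups, with equal correlations among all visits. The residual variance in a baseline-adjusted ANCOVA is (1 + r)/2 − r².
- r = 0.5: 0.75 − 0.25 = 0.50; d* = 0.707; power 71%.
- r = 0.7: 0.85 − 0.49 = 0.36; d* = 0.833; power 83%.

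**5. A calculation that does give the figure.** A one-sided within-group paired test with n = 20 and d = 0.5 on the change scale has noncentrality 0.5 × √20 = 2.236, df 19, critical value 1.729. Power = 69.5%. It matches every stated input, but it tests whether one arm changes from baseline, not whether the combined arm beats a single arm.

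**The case against.** The strongest reply is that 46% belongs to a test the plan does not use for its primary hypothesis. Statistical Analyses assigns t-tests to baseline characteristics and names ANCOVA and repeated measures for the outcome comparisons, and with three assessments those can reach .7. This largely stands. The 46% is a reference point, and it coincides with a planned type of analysis only for a change score, at r = 0.5 or with the effect set on the change scale. It would be wrong to infer that the trial has 46% power, or that .7 is an arithmetic error; the documents do not give enough to show either.

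It can also be said that a repeated-measures analysis of change already uses the baseline score. That is true, but using baseline by subtraction is not the same as adjusting for it: at r = 0.5 the one gives 46% and the other 56%. The covariate wording leaves open which will be done.

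Finally, the spread across methods depends on fixing d in raw-score SD units. That too is correct, and it is why the scale must be stated. On the change-score scale the change-score contrast stays at 46%, so that reading does not rescue the figure.

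A reader might also infer from the 69.5% match that the power was computed for a within-group test. The documents do not say how the figure was obtained, so its origin is unproven.

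**Conclusion.** The point holds as a gap in support, and it should be fixed. With d = 0.5 in raw-score SD units and one-sided alpha 0.05 (both assumed), each primary contrast at a single follow-up has power of about 46% to 70% across the unadjusted, change-score and ANCOVA analyses at r = 0.5 to 0.7. Only the top of that range meets the stated .7, and it requires baseline adjustment together with a correlation of about 0.7; a change score would need about 0.74. A larger effect, a looser alpha or averaging both follow-ups would also reach .7, but the plan states none of these. The figure therefore cannot be tied to the primary hypotheses as written. I am confident about the missing inputs and the calculations; which assumptions the team had in mind cannot be known from the documents.

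**What to change.** Two sentences under Statistical Analyses.

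1. Add: *Each primary ANCOVA will include the baseline score of the same outcome as a covariate.*

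2. Restate power per contrast under that analysis, giving alpha, d and its scale, the visit, and the assumed correlation. For example: *For each contrast (combined vs walking, combined vs CT), with 20 per group, baseline-adjusted ANCOVA of one follow-up, one-sided alpha 0.05 and d = 0.5 in raw-score SD units, power is about 56% to 70% at a baseline-to-follow-up correlation of 0.5 to 0.7 (46% unadjusted).* Alpha, d and r in this example are my assumptions; the team should insert its own.

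If the team intends to analyse the mean of both follow-ups, the plan should say so first; the matching range is then 71% to 83%. If .7 came from another calculation, state which one and how it bears on the between-group contrasts.

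Cost: two sentences, using a baseline score already collected. There is no change to design or enrolment. The downside is that the stated power may become less favourable.

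### Program adherence, which exists only after randomisation, is treated as a baseline characteristic and adjusted for, so the primary comparison can be biased in either direction

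*Combined protocol and SAP*

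**What the plan says.** The Statistical Analyses section states "The groups will be compared on baseline characteristics, including program adherence, using t-tests" and, in the same sentence, that "analyses will be adjusted to account for any observed group differences". Adherence is named in the compared set and nothing exempts it from the adjustment. The ANCOVA and repeated measures comparisons for the primary hypothesis follow in the same paragraph. No unadjusted primary analysis is stated.

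The rest of the protocol places adherence after baseline:

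- Walking: "The walking intervention will begin following baseline assessments and will be continued for 12 weeks".
- Computer training (CT): "Participants will use the program 60 minutes/day, 5 days/week for 12 weeks", with usage tracked as it accrues: "Brain HQ offers a secure clinician portal that allows for monitoring of usage and progress of participants".
- Staff act on adherence while the programme runs: "To guide participants and maintain adherence to the study protocol, the study coordinator will contact the participants weekly".
- The Participants paragraph judges it against the assigned programme: "Participants not showing sufficient adherence to their intervention protocol will be discontinued from the study".
- The combined arm carries both loads: "The combined condition will concurrently follow both the walking and the CT programs as described above".

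No run-in or other pre-randomisation measure of adherence is described. Prior physical activity and the baseline week of step counts are different variables.

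**The concern.** A covariate measured before randomisation cannot be affected by the arm; adherence can. Two things go wrong when it enters the model.

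1. It may lie on the path from assignment to outcome. Comparing arms at equal adherence then removes or adds part of the effect that the trial is meant to estimate.
2. It shares causes with cognition, such as motivation or health. Once adherence is held fixed, participants in the arm where adherence is harder differ on those causes from participants in the other arm, and randomisation no longer protects the comparison.

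The direction depends on which arm adheres more. If the combined arm adheres less, adjustment can create a benefit that does not exist. If it adheres more, adjustment can hide a real one. The covariate is also undefined: adherence means steps in one arm, CT usage in another and both in the third, and the plan sets no common measure.

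**Working it through.** **The plan's own figure.** The plan gives no number for adherence. Its only design figure is power of 0.7 with 20 per group, one-tailed, for a medium effect. Taking medium as 0.5 SD and alpha as 0.05 (neither is stated), a two-sample t-test has noncentrality 0.5/√(2/20) = 0.5/0.316 = 1.58 and power 0.46. The gap between 0.46 and 0.7 is a separate matter; 0.46 is simply the unadjusted reference below.

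**Model (all inputs assumed except 20 per arm).** Combined arm against one single arm, one-sided 5% test. An unmeasured trait U has loading L on both variables:

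- adherence = L·U + √(1−L²)·e₁ + gap·arm
- outcome = L·U + √(1−L²)·e₂ + effect·arm

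Both have SD 1 within arm. Adherence enters the outcome model only if its two-sided t-test gives p < 0.05. The plan says only that observed differences are adjusted for, so adjusting every time is also shown.

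**Always adjusting.** The within-arm slope of outcome on adherence is L², so bias = −L² × gap. For a gap of −0.5 SD:

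- L = 0.3: 0.09 × 0.5 = +0.045 SD
- L = 0.5: 0.25 × 0.5 = +0.125 SD
- L = 0.7: 0.49 × 0.5 = +0.245 SD

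Simulation (40,000 runs per setting) gives +0.045, +0.125 and +0.246 SD, with type I error of about 6%, 10% and 21%.

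**Adjusting only when triggered.** Bias = −L² × P(trigger) × mean observed gap in triggered trials. At a gap of −0.5 SD the trigger fires in 34% of trials, and the mean observed gap in those trials is about −0.83 SD. For L = 0.5 this gives 0.25 × 0.34 × 0.83 = +0.07 SD; for L = 0.7, 0.49 × 0.34 × 0.83 = +0.14 SD.

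| True effect | Gap in combined arm | L | Trigger | Bias (SD) | Rejection rate |
|---|---|---|---|---|---|
| 0 | −0.5 | 0.3 | 34% | +0.03 | about 6% |
| 0 | −0.5 | 0.5 | 34% | +0.07 | about 7.5% |
| 0 | −0.5 | 0.7 | 34% | +0.14 | 11–12% |
| 0 | −1.0 | 0.5 | 87% | +0.23 to +0.24 | 16–17% |
| 0 | +0.5 | 0.5 | 34% | −0.07 | about 3% |
| 0 | +0.5 | 0.7 | 34% | −0.14 | under 2% |
| 0 | 0 | 0.3–0.7 | 5% | 0 | 4–5% |
| 0.5 | +0.5 | 0.5 | 34% | −0.07 | 37% (46% unadjusted) |
| 0.5 | +0.5 | 0.7 | 34% | −0.14 | 30% (46% unadjusted) |

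In this model the unadjusted estimate is unbiased in every row.

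**With adherence also acting on outcome.** Let adherence raise the outcome by 0.3 SD per SD, let the trait load 0.5 on adherence and 0.4 on outcome, and let the gap be 0.8 SD either way, with a true total effect of 0.5 SD. The within-arm slope is 0.3 + 0.5 × 0.4 = 0.5. Always adjusting therefore gives 0.5 + 0.5 × 0.8 = 0.9 SD if the combined arm adheres less, and 0.5 − 0.4 = 0.1 SD if it adheres more. Under the p < 0.05 trigger (6,000 runs) the mean estimates are 0.83 and 0.17 SD, the latter with power 0.13. The unadjusted mean stays at 0.50 SD.

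**The case against.** Five points can be made for the plan.

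- **Loose drafting.** Adherence may have been meant only as something to report by arm. That is possible, but an analyst who follows the sentence would adjust for it.
- **The aim concerns taking part in the programmes,** so an effect among adherers might be intended. Covariate adjustment for observed adherence does not identify that effect unless there are no unmeasured common causes.
- **The unadjusted analysis is not clean either,** because poor adherers are discontinued. The documents do not say whether those participants are still assessed. If they are not, and 20 completers per arm are kept above an assumed cut-off of −1 or −0.5 SD, then with no true effect and a gap of −0.5 SD the unadjusted bias is about +0.05 to +0.08 SD (L = 0.5) or +0.11 to +0.14 SD (L = 0.7). The plan's rule gives about +0.09 to +0.10 and +0.17 to +0.18 SD. This point stands: removing the adjustment then cures less than half of the bias. The unadjusted analysis was still the less biased in every such setting, and the discontinuation rule is a separate defect.
- **The error rates are per comparison.** If the hypothesis requires the combined arm to beat both single arms, the false-positive rate at a gap of −0.5 SD with the trigger is about 2.0% (L = 0.5) or 3.5% (L = 0.7), against 1.2% unadjusted. That is inflation, but below 5%; of these settings, only always adjusting with L = 0.7 exceeds it (9.3%). The protocol does not settle which reading applies.
- **A common scale could be built** as percentage of target, since step goals and CT hours are set. True, but the plan does not do so, and a common scale would not make adherence a baseline variable.

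**Conclusion.** The concern holds and should be corrected before analysis. The text classes a post-randomisation variable as baseline and puts it under a rule that reaches the primary comparison. That conclusion rests on the wording and the protocol's own timeline, not on the simulations.

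The size is unknown. Under the assumed inputs for a moderate case (gap 0.5 SD, loading 0.5 to 0.7, p < 0.05 trigger), the bias is 0.07 to 0.14 SD in either direction, against a standard error of about 0.32 SD at 20 per arm. It is negligible if adherence is only weakly related to outcome, zero if the arms adhere equally, and larger if adjustment is always made, the gap is wider, or adherence itself affects outcome. The claim that the unadjusted analysis is unbiased assumes that everyone randomised is assessed and analysed.

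**What to change.** In the Statistical Analyses section:

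1. Delete the three words that list adherence among the baseline characteristics.
2. State that no variable measured after randomisation enters the primary model.
3. Report adherence descriptively by arm, on each programme's own scale (steps against goal, CT time against schedule), and use it only in an analysis labelled secondary.

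This costs SAP wording only and needs no new data.

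A lesser, separate improvement is to replace adjustment for whatever differences are observed with a short fixed set of covariates already collected at baseline, including at least the baseline value of the outcome; the other members are the sponsor's choice. It costs a few degrees of freedom.

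Neither change resolves the discontinuation of poor adherers in the Participants paragraph. That selection after randomisation needs to be addressed separately.
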